7.1.5 Missing Data Handling

In general, no imputation of missing data is planned for the primary analyses. However, for purposes of any sensitivity analyses, missing data may be imputed using last-observation-carried forward, or other advanced statistical imputation methods.

For the efficacy analyses based on oxygenation parameters, up to Day 6, if the assessment on Day 6 is not available, then the last prior non-missing value, after baseline will be used. See Sections 7.1.2, 7.1.3, and 7.1.4 for algorithm on determining assessments to be used for analysis.

Imputation for P(A-a)O₂ gradient, intubation rate and ordinal scale will not be performed.

If using last observation carried forward, a missing follow-up visit value will be imputed as that patient's previously observed value.

In the absence of any other specifications, the following rule will be used for missing time-toevent data:

• Patients who are alive (not lost to follow up) and did not experience the event of interest will be censored at the date last known to be alive and to be event-free.

7.2 Sample Size

Approximately 120 patients will be randomized: of which 80 will receive sargramostim + SOC, and 40 patients who will receive SOC alone to evaluate the clinical efficacy and safety of sargramostim in patients with COVID-19 associated acute hypoxemia.

The sample size was based on practical and clinical considerations to ensure that the efficacy endpoints and safety profile could be appropriately evaluated and was not based on any statistical assumptions or hypotheses. As a result, the analyses of this study will be considered as descriptive analyses.

7.3 Data Safety Monitoring Board

The DSMB will comprise of independent external experts to review the safety and benefit/risk data. See Section 12.2 of the Study Protocol and/or DSMB Charter for further information.

7.4 Analysis Population

The following analysis populations will be used to summarize the results from this study.

- Safety Population includes all patients who received at least one dose of sargramostim and/or SOC based on actual treatment received. Patients who did not receive any study treatment (either sargramostim and/or SOC) will be excluded from Safety Population. All safety analyses will be based on the Safety Population.
- Intent-to-treat Population (ITT) includes all patients who were randomized, and analyzed per the treatment arm as randomized. Selected efficacy analysis (P(A-a)O₂ and intubation rate) may also be performed based on ITT population for the purpose of sensitivity, unless otherwise specified.
- Modified Intent-to-treat Population (MITT): a subset of the ITT population that received at least one dose of any study treatment (either sargramostim and/or SOC). Efficacy analyses will be based on the MITT Population.
- **Per Protocol Population (PP)** includes all patients who were randomized and received at least one dose of sargramostim and/or standard of care based on the treatment assigned

at randomization and meet the eligibility criteria of this study. Selected efficacy analyses may also be performed based on the Per Protocol Population, unless otherwise specified.

- If the ITT, and PP populations are identical, or less than 10% different compared to the MITT population, then the selected efficacy analyses may not be repeated across the ITT and PP analysis population.
- Enrolled Population includes all patients who were eligible and signed informed consent form (ICF).

7.5 Patient Disposition

Descriptive statistics by treatment will be used to summarize the number of patients enrolled, the number of screening failures, the number of patients in Safety Population, ITT, MITT, and PP, number of patients who completed key study timepoints of interest (Days 1-5, Up to Day 6, Day 14, Day 28, Day 58), and who completed treatment period, completed the study, withdrew from treatment, and withdrew from the study, and reasons for withdrawals from treatment and from study. The descriptive statistics will include numbers and percentages of patients in each identified category by treatment arms. A patient's data listing will be provided for disposition that includes patients who are excluded from each analysis populations (and reasons for exclusion); who prematurely withdrew from the study and for early treatment discontinuation, along with the associated reasons.

7.6 **Protocol Deviations**

All reported protocol deviations will be reviewed, and determined to be major or minor, based on the potential impact to efficacy and/or safety.

A subject listing of protocol deviations data will be presented.

The following general categories will be considered major deviations include, but are not limited to:

- Deviation 1: Patients randomized but who did not receive study drug or standard of care (i.e., not treated)
- Deviation 2: Patients who deviate from the following key entry criteria:

- Inclusion:
- Exclusion:
- Deviation 3: Patients randomized who received treatment other than that to which they were randomized to (i.e., received the other treatment).

7.7 Demographics and Baseline Disease Characteristics

Demographic information for MITT Population will be summarized. The demographic data consists of age, gender, race, ethnicity, baseline height, body weight, body mass index (BMI), Body Surface Area (BSA). The baseline disease assessment scales, including the SOFA score (including categorization of <6 versus \geq 6), ordinal scale, and National Early Warning System 2 Score will be summarized. The baseline COVID-19 diagnostic information will also be summarized.

Individual demographics and other baseline factors will be listed by patient.

Continuous variables (for example, age, height, body weight, body mass index, body surface area, disease assessment scales) will be summarized by n, means, medians, minimum, maximum, and 25^{th} and 75^{th} percentiles. Number of patients and percentages will be used to describe categorical (discrete) variables (for example, gender, race, ethnicity and SOFA score <6 versus ≥ 6).

If there is a difference between the MITT and the Safety Population, the summary of baseline and disease characteristics may be repeated on the Safety Population.

7.8 Medical History

Medical condition and/or significant medical history will be coded using Medical Dictionary for Regulatory Activities (MedDRA) Version 23.0 or later, and listed by reported term, System Organ Class and Preferred Term (PT). The number and percentage of patients will be summarized by System Organ Class and PT by treatment for MITT Population, and listed.

7.9 Concomitant Medications

All medications will be coded using WHO Drug Enhanced Dictionary (March 2020 Version or later) and categorized as Prior Medication, Concomitant Medication, or Post Medication based on the following:

- Prior medications include medications that have a start date and end date before the date/time of the first dose of the study treatment;
- Concomitant medications include medications that start date prior to, or after the date of first dose, that is administered any time through Day 58 and could continue on into follow up period;
- Post medications include medications that have a start date after Day 58.

Depending on the start and end date/time, medications are categorized as prior, concomitant, or post, as displayed in Figure 1 below.

Figure 1: Concomitant Medication Categorization

Concomitant medications will be summarized by treatment, Anatomical Therapeutic Chemical (ATC) classes, and Preferred Term for MITT Population. Prior and Post Medications will be included in the patient's listing of medications including the start and end dates, prior/concomitant/post flag, whether it is ongoing, dose, unit and indication.

Standard of Care treatments for COVID-19 will be tabulated separately from other concomitant medications. These treatments may be given prior to entry into study, or during the study.

7.10 Extend of Exposure and Treatment Compliance

Study days, including first and last dose, to enable deviation of treatment durations for both treatment arms are defined in Section 7.1.1.

Treatment duration and treatment compliance will be summarized for the Safety Population. For each patient, the treatment duration is defined as the number of days from the first treatment date to the last treatment date, and can be calculated as:

Treatment Duration (Days) = (Date and Time of Last Treatment – Date and Time of First Treatment)/24 +1.

The result of treatment duration will be rounded to the nearest integer. For example, if the calculation results in 5.4 days, then the final result of treatment duration will be 5 days.

See Section 7.1.4 for handling missing treatment times. Otherwise, if time of the last treatment is not available, the end time of the treatment duration will be imputed using the earliest of 1) End time of treatment Day 5; or 2) Time of patient's early discontinuation from the treatment or from the study (where available). Treatment duration will be calculated for both treatment arms, and will include any treatment, sargramostim, and standard of care durations.

For each patient who received sargramostim, the treatment compliance is defined as the actual treatment received as percentage of the planned treatment (K days). It can be calculated as:

Treatment Compliance = 100*(Treatment Duration– Number of Days without Study Treatment)/K

In this study, the prespecified treatment duration of sargramostim is 5 days (K=5).. For discontinued patients, K would be equal to the number of days from the date the sargramostim study drug is first received to the date of early discontinuation.

K can be smaller than 5 1) if the end of the treatment/early discontinuation of treatment before Day 5; 2) if the patient has not completed 5 days of sargramostim treatment and has not discontinued treatment/study early by the time of the data cut.

Since there is no planned or prespecified treatment duration for the standard of care therapies, compliance with standard of care cannot be determined or summarized.

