7.1.4 Post-Treatment: Up to Day 6 (or Discharge, whichever is earlier)

The post-treatment evaluation is one of the main timepoints for evaluation of efficacy endpoints, particularly measures of oxygenation. In the protocol, this is referred to as the Day 6 evaluation. In the context of this document, this will be presented as "Up to Day 6".

For the **sargramostim arm**: any assessment that is performed within 24 hours after the last treatment administration date/time may be considered as the "Up to Day 6" evaluation. That is, within last dose date/time + 24 hours. If there are no assessments in that timeframe, then the last

post-baseline observation prior to last dose date/time will be used. To address any missing dose times for the known dose dates:

- if the start time of inhalation dosing is known, then the end time can be assumed to be 15 minutes later (i.e., end time = start time + 15 minutes)
- otherwise, the end time will be assumed to be 23:59

For patients who received **standard of care alone**, any assessment that is within 1 calendar day after the later of, the treatment completion (or treatment discontinuation date) [from the treatment disposition CRF page] or Day 6/Post-Treatment visit date, may be considered as the "Up to Day 6" evaluation. If there are no assessments in that timeframe, then the last postbaseline observation prior to latter of, the treatment completion (or treatment discontinuation date) or Day 6/Post-Treatment visit date, will be used.

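### SAP Section 7.10: compliance is called a percentage of the planned 5 days, but K is reset for patients who stop early, and adding 1 to a clock-time difference can score a full course 80% or 120%

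*SAP*

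**What the plan says.** All the rules are in SAP Section 7.10, apart from the handling of missing times.

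- **Meaning of compliance:** "the treatment compliance is defined as the actual treatment received as percentage of the planned treatment (K days"). The planned length is set at 5 days, so K = 5.
- **Formula:** "Treatment Compliance = 100*(Treatment Duration– Number of Days without Study Treatment)/K".
- **Change of K:** "For discontinued patients, K would be equal to the number of days from the date the sargramostim study drug is first received", running to early discontinuation. The section confirms that K may be below 5 when treatment ends before Day 5, or when a patient is still on treatment at a data cut.
- **Duration in words:** "the treatment duration is defined as the number of days from the first treatment date to the last treatment date".
- **Duration as a formula:** "Treatment Duration (Days) = (Date and Time of Last Treatment – Date and Time of First Treatment)/24 +1".
- **Rounding:** "The result of treatment duration will be rounded to the nearest integer". The example given is "if the calculation results in 5.4 days, then the final result of treatment duration will be 5 days".
- **Missing dose times (Section 7.1.4, to which 7.10 refers):** with a known start time, the end is set 15 minutes later; "otherwise, the end time will be assumed to be 23:59".

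No cap at 100% is stated. Nor does the SAP say whether K includes both end dates.

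**The concern.** There are two separate faults.

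First, the denominator contradicts the definition. A percentage of planned treatment needs the plan underneath it. Once K shrinks to the time until discontinuation, the figure describes adherence before stopping, yet it would still be labelled and read as a share of the plan.

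Second, the duration formula mixes two conventions. An inclusive plus 1 is right for calendar dates, and the SAP uses it that way for study day (Section 7.1.1) and for hospital stay (Section 7.11.2.5). Here it is added to an elapsed clock time and the result is rounded, so time of day can move a five-day course up or down by a whole day.

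What is at stake is how the exposure table is read. The Per Protocol set in Section 7.4 requires only one dose, so no analysis set screens out patients who received little drug. The duration and compliance summaries are where a reader looks for how much was delivered.

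**Working it through.** **Inputs (SAP Sections 7.10 and 7.1.4).** D = round(elapsed hours / 24 + 1); compliance = 100 × (D − days without treatment) / K; planned K = 5; unknown time = 23:59.

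**The SAP's own figure.** 5.4 rounds to 5, as stated. Dosing at the same clock time on Days 1 and 5 gives 96/24 + 1 = 5 days, or 100%. The rules work in that case.

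**Early stopping.** Assume the same clock time each day and no missed day before the last dose, so D equals the last dosing day. The SAP does not say how K is counted, so four readings are shown.

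| Last dose | Share of planned 5 | Stop dated same day, K inclusive | Stop dated next day, K inclusive | Same day, plain date difference | Next day, plain date difference |
|---|---|---|---|---|---|
| Day 1 | 20% | 1/1 = 100% | 1/2 = 50% | 1/0, undefined | 1/1 = 100% |
| Day 2 | 40% | 2/2 = 100% | 2/3 = 66.7% | 2/1 = 200% | 2/2 = 100% |
| Day 3 | 60% | 3/3 = 100% | 3/4 = 75% | 3/2 = 150% | 3/3 = 100% |
| Day 4 | 80% | 4/4 = 100% | 4/5 = 80% | 4/3 = 133% | 4/4 = 100% |

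Only one cell, a Day 4 stop dated Day 5 with inclusive K, agrees with the planned share. The inclusive count is the one consistent with the study-day rule in Section 7.1.1.

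**Group illustration.** The documents give no stopping rate. Assume that 20% stop after Day 2 and the rest score 100%. Against plan, the mean is 0.8 × 100 + 0.2 × 40 = 88%. As written, it is:

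- 0.8 × 100 + 0.2 × 100 = 100% (same day, inclusive; or next day, plain difference)
- 0.8 × 100 + 0.2 × 66.7 = 93.3% (next day, inclusive)
- 0.8 × 100 + 0.2 × 200 = 120% (same day, plain difference)

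**Full course, dosed on every one of Days 1 to 5, K = 5.**

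| First dose | Last dose | Hours | Hours/24 + 1 | D | Compliance |
|---|---|---|---|---|---|
| Day 1 21:00 | Day 5 08:00 | 83 | 4.46 | 4 | 80% |
| Day 1 20:00 | Day 5 09:00 | 85 | 4.54 | 5 | 100% |
| Day 1 10:00 | Day 5 10:00 | 96 | 5.00 | 5 | 100% |
| Day 1 08:00 | Day 5 20:00 | 108 | 5.50 | 6 | 120% |
| Day 1 10:00 | Day 5 23:59 (imputed) | 109.98 | 5.58 | 6 | 120% |
| Day 1 12:00 | Day 5 23:59 (imputed) | 107.98 | 5.499 | 5 | 100% |

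The unrounded value for such a course runs from about 4.00 to about 6.00. Six days needs at least 96 + 12 = 108 hours. Four days needs fewer than 96 − 12 = 84 hours; at exactly 84 hours the value is 4.5, and the result depends on how halves are rounded. With one missed day, the same clock-time effect gives 60%, 80% or 100%.

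**After the fix.** Last date − first date + 1 is 5 for every Day 1 to Day 5 course, whatever the times. With K = 5 and no missed day, stops on Days 1 to 4 give 20%, 40%, 60% and 80%.

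**The case against.** **The smaller K is deliberate.** Section 7.10 says openly that K can fall below 5 and when. Adherence up to discontinuation, kept apart from persistence, is a legitimate quantity. That stands as a choice of measure. It does not reconcile the rule with the section's own definition, and the measure still needs a counting rule for K.

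**K is not days on drug.** It runs to the discontinuation date, so a reader might infer too much in saying that early stopping can never lower compliance. A last dose on Day 2 with discontinuation dated Day 4 gives 2/4 = 50% under an inclusive count. Stopping can lower the figure, but not reliably to the planned share.

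**Early stopping is visible elsewhere.** Section 7.10 also summarises duration. Section 7.5 tabulates, by arm, completion of Days 1-5 and of the treatment period, and withdrawals from treatment with reasons. A reader might infer that poor delivery would be hidden; the documents do not support that.

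**The clock-time fault may be rare.** Rounding absorbs shifts of less than 12 hours. Section 6.5 leaves administration to the protocol, so the frequency cannot be judged here. The 23:59 rule applies only when the start time is also unknown, and it produces 6 days only if the first dose was before about noon. If both times are set to 23:59, the result is exactly 5. All this stands, but the formula remains wrong for the courses it does affect.

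**Conclusion.** The point holds as a fault in stated rules. For patients who discontinue, compliance is not the percentage of planned treatment that the SAP says it is. Under an inclusive K with same-day discontinuation it overstates the planned share by 80, 60, 40 and 20 percentage points for stops on Days 1 to 4. Other readings give smaller overstatements, larger ones, or no value at all, so two programmers could produce different tables. Separately, a course dosed on all five days can score 80% or 120% when first and last clock times are about 12 hours or more apart.

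The early-stop figures assume equal clock times and no missed days. The 88% against 100% comparison is illustrative only, because its 20% stopping rate is assumed.

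The effect is confined to the descriptive exposure and compliance summary. A reader might infer that the efficacy conclusions are affected. They are not: no analysis population in Section 7.4 has a compliance threshold, no planned efficacy analysis uses compliance, and Sections 7.1 and 7.2 treat all analyses as descriptive. Nor is the plus 1 wrong in itself; the fault is adding it to a clock-time difference and then rounding.

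**What to change.** In Section 7.10:

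1. Compute duration as last dose date − first dose date + 1 on calendar dates, without times or rounding. This also removes the need for the 23:59 rule in this calculation.
2. Keep K = 5 for every sargramostim patient, including those who discontinue. The only exception is a patient still on treatment at a data cut, for whom the counting rule for K should be written out with both end dates included.
3. Compute compliance as days with sargramostim administered / 5. If the protocol plans more than one administration per day, use administrations received / administrations planned, since a day count would then miss partly dosed days.

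If adherence up to discontinuation is also wanted, report it as a second figure under that name, with the K count defined.

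The cost is a short SAP edit and simpler programming. No data collection changes. The compliance figure will be less favourable if patients stop early.

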7.11 Efficacy Evaluations

The primary and secondary efficacy endpoints of the study (as defined above in Sections 5.2.1 and 5.2.2 above) will be analyzed as specified below. If the primary and secondary efficacy endpoints show meaningful results, then the exploratory efficacy endpoints (Section 5.2.3 above) will be summarized.

Key timepoints of interest for endpoints include Days 1-6, Day 14, and Day 28, where data are assessed and/or available, unless otherwise specified. All available efficacy data will be tabulated and presented for all patients in the Modified Intent-to-Treat (MITT) Population; see Section 7.4.

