7.11.3.1 National Early Warning Score (NEWS-2)

The calculated total National Early Warning Score (NEWS-2) (See the scoring in Appendix D of the Study Protocol) will be summarized by treatment arm for each available timepoint of interest using descriptive analyses. Individual measures and overall score will be provided in patient data listing.

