7.11.3.2 Sequential Organ Failure Assessment (SOFA)

Sequential Organ Failure Assessment (SOFA) are based on six different scores, including respiratory, cardiovascular, hepatic, coagulation, renal, and neurological systems. The overall calculated SOFA score will be summarized by treatment arm for each available timepoint.

Individual SOFA scores and its components such as the Glasgow Coma Score will be provided in a patient data listing.

The Glasgow Coma Score and the SOFA Scores are defined in Appendices A and B of the Study Protocol, respectively.

7.11.3.3 **ROX Index**

The ROX Index assessment is described in Appendix E of the Study Protocol.

ROX Index calculation = SpO₂/FiO₂ ratio/ Respiratory rate (breaths/min).

The ROX Index will be summarized by treatment arm . The ROX Index Score and its components will be listing by patient.

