7.11.3.4 ARDS progression and Changes on Chest X-ray or CT

The exploratory endpoints of progression to ARDS and changes on chest x-ray or CT will be evaluated in terms of determining ARDS progression.

Chest X-ray or CT may be performed at the Screening visit, Treatment period Days 1-5, Posttreatment period at Day 6 or day of discharge (whichever is earlier), Days 7-27 (or until hospital discharge), Day 28, and Day 90.

Percentage of patients in whom ARDS or ARDS progression is documented post-baseline will be summarized. Potential available data sources for the diagnosis of ARDS/ARDS progression include adverse events, physical examination findings, imaging studies such as Chest X-ray, CT, treatment or study discontinuation reasons, etc.

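### Section 7.11 makes the exploratory summaries depend on undefined meaningful primary and secondary results, contradicts the plan's own unconditional text, and so permits them to be omitted after a neutral or unfavourable result

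*SAP*

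**What the plan says.** Section 5.2.3 lists five exploratory endpoints: NEWS-2, SOFA, the ROX Index, progression to ARDS, and changes on chest X-ray or CT. The first paragraph of section 7.11 attaches a condition to them: "If the primary and secondary efficacy endpoints show meaningful results, then the exploratory efficacy endpoints" of that section are to be summarized.

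The second paragraph of the same section carries no condition: "All available efficacy data will be tabulated and presented for all patients in the Modified Intent-to-Treat (MITT) Population; see Section 7.4".

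The subsections of 7.11.3 are also unconditional:

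- **NEWS-2 (7.11.3.1):** the total score "will be summarized by treatment arm for each available timepoint of interest using descriptive analyses", and "Individual measures and overall score will be provided in patient data listing".
- **SOFA (7.11.3.2):** "The overall calculated SOFA score will be summarized by treatment arm for each available timepoint", with a listing of scores and components.
- **ROX (7.11.3.3):** a summary by arm and a listing by patient.
- **ARDS and imaging (7.11.3.4):** "Percentage of patients in whom ARDS or ARDS progression is documented post-baseline will be summarized". Imaging is assessed as part of determining ARDS progression. No listing is named.

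Sections 7.1 and 7.2 treat every analysis as descriptive. Confidence intervals and p-values are produced where applicable, but no decision rule is tied to them.

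**The concern.** Whether a pre-specified endpoint is summarized should not turn on what the other endpoints show. Here it does, through a judgement that the plan does not define. A condition based on data availability would be neutral, and section 8.1 already deals with that case by printing a shell marked as empty. The condition in 7.11 is different in kind because it looks at the results.

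Gating can be justified when it protects the error rate of confirmatory tests. Nothing here needs that protection: the plan makes no confirmatory claim, and 7.11.3 specifies no test for any exploratory endpoint.

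The trial is open-label, and the SAP's opening section requires it to be final only before database lock. An undefined choice about which comparative tables appear is therefore a practical route to selective reporting. ARDS progression and post-baseline SOFA can show deterioration as well as benefit, and a reader would want them most if the primary result were neutral or unfavourable.

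**Working it through.** The plan gives no figure to reproduce, so the check is mainly one of text against text.

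**1. Is the trigger defined?** No. Section 7.11 does not say what counts as meaningful, in which direction, or how many endpoints must qualify. Section 7.2 rules out any statistical hypothesis behind the sample size, and no alpha is stated. The word is also used in 7.11.1.1, but there it concerns a patient's percentage improvement in P(A-a)O₂ gradient, and the cutoff can move (33%, with 25% or 50% as alternatives). That cannot serve as a criterion for a trial result.

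**2. Do the instructions agree?** Take a neutral trial.

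| Text | By-arm exploratory summaries after a neutral result |
|---|---|
| 7.11, first paragraph | Not promised |
| 7.11, second paragraph | All available efficacy data presented |
| 7.11.3.1 to 7.11.3.4 | NEWS-2, SOFA, ROX and ARDS progression summarized |

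Two programmers working from this plan could produce different table sets, each with text to support it.

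**3. What remains if the condition is applied strictly?**

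| Endpoint | By-arm post-baseline summary | Dedicated patient listing |
|---|---|---|
| NEWS-2 | Can be omitted | Kept (7.11.3.1) |
| SOFA | Can be omitted | Kept (7.11.3.2) |
| ROX | Can be omitted | Kept (7.11.3.3) |
| ARDS progression, including imaging | Can be omitted | None named (7.11.3.4) |

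Baseline SOFA and NEWS-2 are summarized under section 7.7 in any case.

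**4. How much does the vagueness matter?** This is an illustration only. It assumes no treatment effect, independent endpoints, and meaningful taken as p below a threshold a. None of this is in the SAP, and the endpoints are unlikely to be independent. Section 5.2 lists 2 primary and 10 secondary endpoints, 12 in all, or 11 without the secondary endpoint on serious adverse events and drug reactions. The chance that the condition is met is a² if both primaries must qualify, and 1 − (1 − a)^k if any one of k endpoints suffices.

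| Reading of the trigger | a = 0.05 (two-sided) | a = 0.025 (favouring sargramostim only) |
|---|---|---|
| Both primaries | 0.05² = 0.0025 | 0.025² = 0.0006 |
| Either primary | 1 − 0.95² = 0.0975 | 1 − 0.975² = 0.049 |
| Any of 11 | 1 − 0.95¹¹ = 0.43 | 1 − 0.975¹¹ = 0.24 |
| Any of 12 | 1 − 0.95¹² = 0.46 | 1 − 0.975¹² = 0.26 |

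Under the same null data, the condition could be met almost never or nearly half the time, depending on how one sentence is read. The figures show that the rule cannot be applied reproducibly. They do not measure bias in any estimate.

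**The case against.** The strongest reply is that the sentence says when the summaries will be produced and never says they are dropped otherwise. A reader might infer that the endpoints are summarized only if the results are meaningful, and that the plan will suppress all five after a negative trial. The documents do not support that. The wording gives a sufficient condition, the next paragraph points the other way, and three of the endpoints keep listings.

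The reply can be pressed as a dilemma. If the opening of 7.11 governs its subsections, then 7.11.3 only describes how the summaries would be made, and much of the contradiction goes. If 7.11.3 stands alone, the summaries are produced and nothing is lost. This is fair against any claim of certain loss. It does not rescue the plan, because the plan does not say which reading applies, and on the first reading the second paragraph of 7.11 still conflicts.

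It is also true that harm would be visible elsewhere. ARDS recorded as an adverse event reaches the tables of 7.12.1. Intubation (7.11.1.2), the ordinal scale (7.11.2.1), mortality (7.11.2.2), the oxygenation ratios (7.11.2.3), laboratory values (7.12.2) and vital signs (7.12.4) are all reported without this condition. That limits the damage. It does not replace the ARDS progression summary, which also draws on imaging, physical examination and discontinuation reasons.

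A reader might further infer that exploratory effects reported after a favourable primary result are inflated. Some overlap is plain, since ROX uses SpO₂/FiO₂, itself a secondary parameter. But the plan gives no correlations from which to size any inflation. The condition also says meaningful rather than favourable, so a clearly adverse result might meet it. The inflation claim is not shown.

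**Conclusion.** The point holds as an undefined, result-dependent reporting condition that contradicts unconditional text in the same section and in 7.11.3. It permits omission and does not order it. Its reach is four by-arm summaries in about 120 patients (80 + 40), with ARDS progression the most exposed. No primary or secondary estimate, safety output, error rate or sample size depends on it.

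The conclusion rests on the wording alone and needs none of the assumptions behind the illustrative probabilities. It should be corrected before database lock, as a modest change to exploratory reporting in a descriptive Phase 2 trial.

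**What to change.** Replace the conditional sentence in section 7.11 with:

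> Exploratory efficacy endpoints (Section 5.2.3) will be summarized by treatment arm as described in Section 7.11.3, regardless of the primary and secondary results.

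This settles the conflict in favour of what the second paragraph of 7.11 and section 7.11.3 already promise. If the sponsor meant the condition to apply only to further inferential work on these endpoints, the plan should say so and define the criterion before database lock.

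The cost is one sentence and a few descriptive tables from data already collected.
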